### **2.2 Secondary objectives**

The secondary objectives of this study are:

- to assess the difference between esomeprazole and placebo in the treatment of symptomatic reflux episodes of GERD.

- to assess the difference between esomeprazole and placebo in the treatment of other GERD-related signs and symptoms via video, pH/impedance, and cardiorespiratory monitoring
- to assess the efficacy of esomeprazole, compared to placebo, in reducing the number of (a) all types of reflux episodes (acid or non-acid) and (b) acidic reflux episodes, defined as pH < 4, via pH/impedance monitoring
- to assess the safety and tolerability of esomeprazole compared to placebo

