### **3.1.6 pH/intraluminal impedance/video monitoring**

Placement of the pH/impedance probe will be scheduled so that it coincides just prior to feeding time if possible. If necessary, a separate feeding tube may be placed beside the pH/impedance probe, through which the investigational product may be given to the patient. (See Section 3.4.2)

Esophageal pH/intraluminal impedance will be measured and recorded for a total of 18 - 24 hours using the Sandhill Scientific Insight System. A portion of this (8 hours) will be integrated with the Respironics Alice 5 Diagnostic Sleep System, and will include measurement of cardiorespiratory data such as respiration rate, heart rate, ECG and oxygen levels, as well as video, sound and movement monitoring. A synchronizing device, developed for this study, will be used to integrate the data. Video will be recorded for 8 hours (approximately) and approximately 6 hours should be considered evaluable, which is defined as having a clear image, the camera pointed at the child, and the face and upper body are visible. The 8 hours of video should ideally include at least 2 feedings and include dosing on the final study day (2 hours before and 6 hours after dosing). Every attempt should be made to collect baseline and final study day evaluations during the same time of day.

This 8 hours of data will be downloaded onto a computer and then stored on 2 duplicate sets of 2 DVDs (or equivalent media), each labelled with patient identifier information. One set of DVDs will be kept at the study site and the other will be sent to the AstraZeneca contract research organization (CRO) data management representative.

The study nurse or qualified site personnel (ie, medical or nursing staff) will prepare surveillance notes while the monitoring is occurring. Comments from the surveillance notes will be marked on the integrated system during the review process for both the baseline and final study day visits.

The site will review the video to ensure that approximately 6 hours are considered evaluable before randomization of the patient. Patients without approximately 6 hours of evaluable video at baseline will be discontinued.

Qualified site personnel will also review the 8 hours of pH/impedance data recorded during the video monitoring and mark events in the system where applicable.

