A qualified reader, (either a central reader or site specific as applicable) per standard guidelines, will review the 8 hours of all the integrated data (cardiorespiratory monitoring, pH, impedance and video) and document any correlations between the events and the presence of reflux. The start and stop time of events will be determined so that durations can be calculated. The reader who will be reviewing the integrated data, as well as all site personnel, will be blinded to the investigational product assigned to the patient.

The 18 – 24 hour pH/impedance data will be used to calculate the reflux index in those patients that complete this procedure. However, as long as patients have completed the 8 hours of video monitoring, they will be considered evaluable regardless of whether they complete the remaining pH/impedance monitoring.

The following assessments of all types of reflux episodes (acid or non-acid) will be made at baseline and after treatment using standard reports from the pH/intraluminal impedance monitoring:

[figure not shown]
- acidic GER episodes (pH<4)

- weakly acidic GER episodes (pH 4 – 6.9)
- non acidic GER episodes (pH $\geq$ 7)
- liquid GER episodes
- mixed gas/liquid GER episodes
- mean bolus clearance time
- mean acid clearance time

The following assessments of acidic reflux episodes will be made at baseline and after treatment using the standard reports from the esophageal pH probe based on the entire time of pH monitoring:

- number of acidic reflux episodes (pH<4)
- number of acidic reflux episodes greater than 5 minutes
- % time pH < 4
- % time pH 4 – 6.9

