**Table 3 Study objectives and endpoints**

Objective	Endpoint	Summary statistic for analysis	Analysis method

Secondary: to assess the efficacy of esomeprazole, compared to placebo, in reducing the number of
 
(a) all types of reflux episodes (acid or non-acid)
 
(b) acidic reflux episodes, defined as pH < 4, via pH/impedance monitoring
	
Secondary:
 
(a) from impedance data: separately for baseline and after treatment period: Numbers of acidic episodes, weakly acidic episodes, non-acidic episodes, liquid GER episodes, mixed gas/liquid GER episodes, mean bolus clearance time, mean acid clearance time
 
(b) from pH data separately for baseline and after treatment period: number of acidic reflux episodes (ie, pH<4), number of episodes lasting longer than 5 minutes, %time pH<4, %time pH 4-6.9 (inclusive)
	
Secondary:
 
(a) mean change from baseline in mean number of episodes and clearance time by treatment group
 
(b) mean change from baseline in numbers of acidic reflux, in episodes lasting longer than 5 minutes, in %time pH <4, in %time pH 4-6.9 (inclusive), by treatment group
	
Secondary: Descriptive statistics will be provided for the endpoints of interest.

Secondary: To assess the safety and tolerability of esomeprazole compared to placebo
	
Secondary: Adverse events, and change from baseline in clinical laboratory parameters and vital signs
	
Secondary: mean percentage of patients with AEs, changes from baseline in lab parameters and vital signs by treatment group
	
Secondary: Descriptive statistics

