#### 4.6.1 Esophageal pH and intraluminal impedance monitoring

Combined esophageal pH and intraluminal impedance monitoring assessments will be performed for 18 – 24 hours twice during the study. The first one will be carried out at the baseline visit. The second pH-monitoring assessment will be made on the final study day.

The 18 – 24 hour pH/impedance data will be used to calculate the reflux index in those patients that complete this procedure. However, as long as patients have completed the 8 hours of video monitoring, they will be considered evaluable regardless of whether they complete the remaining pH/impedance monitoring.

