#### 4.6.1.2 Calculation or derivation of outcome variables

The following pharmacodynamic variables will be calculated for each patient and recording period:

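### pH-probe reflux episode counts are raw numbers over recordings of unequal length; they should be scaled to recorded time and given a between-arm estimate

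*Protocol*

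**What the plan says.** - **Objective.** Protocol Section 2.2 sets out "to assess the efficacy of esomeprazole, compared to placebo, in reducing the number of (a) all types of reflux episodes" and of acidic episodes. It concerns numbers of episodes and is comparative.
- **Recording length.** Section 3.1.6: "Esophageal pH/intraluminal impedance will be measured and recorded for a total of 18 - 24 hours". This applies at baseline and on the final study day.
- **Shortest recording.** Sections 3.1.6 and 4.6.1 say of patients who have completed the 8 hours of video that "they will be considered evaluable regardless of whether they complete the remaining pH/impedance monitoring". The reflux index is limited to patients who complete the 18 to 24 hours; no such limit is stated for the episode counts.
- **Time base.** Section 3.1.6 takes the pH-probe variables "using the standard reports from the esophageal pH probe based on the entire time of pH monitoring". The impedance list in the same section names no window. Section 4.6.1.2 says that the variables of both lists "will be calculated for each patient and recording period".
- **Summary and method.** Table 3 gives, for the pH data, "mean change from baseline in numbers of acidic reflux, in episodes lasting longer than 5 minutes" and in the two percentage-time measures, by treatment group. The method is: "Descriptive statistics will be provided for the endpoints of interest". The synopsis and Section 6.4 also call for descriptive statistics only.
- **Deferral.** Section 6.1 leaves calculation of derived variables and handling of missing data to the SAP, which is not at hand.

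**The concern.** A count over a recording is the reflux rate multiplied by the hours recorded. The plan fixes the count, allows the hours to vary between infants and between an infant's two visits, and nowhere divides one by the other. The reported change from baseline therefore mixes a change in reflux with a change in recording time.

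The protocol handles its other variables differently. Sleep, quiet and crying time become percentages of time. Symptom counts come from a nominally fixed 8-hour window. Both are compared between arms by ANCOVA with the baseline value as covariate. The reflux counts get neither the scaling nor the comparison, although their objective names the number of episodes and names placebo.

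At stake is how well this objective can be read. These counts are the direct measure of whether treatment reduced the number of acid reflux episodes, which helps in interpreting the primary symptom result.

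**Working it through.** **The plan's own figure.** The protocol gives no rate, power or sample size for the reflux counts. Its 38 per group (Section 6.5) concerns the primary variable: n = 2 × (1.960 + 0.842)² × 1.5² = 35.3, so 36 per group by the normal approximation and 37 by the t-test. At 38 the t-test power is 81.8%, so the figure reproduces. It does not bear on this point beyond supplying an arm size for step 4.

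**1. Length alone (protocol durations only).** Expected count = hourly rate × hours. At a constant rate the ratio of final to baseline count is the ratio of hours:

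| Baseline h | Final h | Ratio | Change in count |
|---|---|---|---|
| 18 | 24 | 24/18 = 1.33 | +33% |
| 24 | 18 | 18/24 = 0.75 | −25% |
| 24 | 8 | 8/24 = 0.33 | −67% |
| 8 | 24 | 24/8 = 3.00 | +200% |

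**2. Within-arm change.** Assume that full recordings average 21 h and that 10% of final recordings stop at 8 h in both arms. Mean final hours = 0.9 × 21 + 0.1 × 8 = 19.7, and 19.7/21 = 0.94. Each arm then shows a fall of about 6% with no change in reflux.

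**3. Between-arm contrast, equal lengths.** Take a true 30% reduction on esomeprazole and none on placebo, with 18 h at baseline and 24 h at the end in both arms. Final over baseline is 0.70 × 24/18 = 0.93 on esomeprazole and 24/18 = 1.33 on placebo. The between-arm ratio is 0.93/1.33 = 0.70, so the effect survives. The within-arm figure of −7% is misleading; the contrast is not.

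**4. Between-arm contrast, simulated with no drug effect.** The assumptions are not from the protocol: 38 per arm, 1 episode per hour, between-patient CV 0.5, full recordings uniform on 18 to 24 h, and a t-test on change from baseline.

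| Final recordings stopped at 8 h (one arm / other arm) | False difference in raw counts | Type I error, raw counts | Type I error, per hour |
|---|---|---|---|
| 0% / 0% | about 0 | 4.8% | 5.4% |
| 10% / 10% | about 0 | 5.3% | 5.1% |
| 10% / 20% | 1.3 episodes | 9.9% | 5.0% |
| 10% / 30% | 2.6 episodes | 24.8% | 4.8% |

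The false differences agree with direct arithmetic. Mean final hours are 19.7 at 10% short, 0.8 × 21 + 0.2 × 8 = 18.4 at 20%, and 0.7 × 21 + 0.3 × 8 = 17.1 at 30%. At 1 episode per hour the gaps are 19.7 − 18.4 = 1.3 and 19.7 − 17.1 = 2.6. The arm with more short recordings appears to have less reflux. The per-hour difference is about 0 in every row.

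**5. Noise, equal lengths (same assumptions).** The SD of change in raw count is 6.5 with a fixed 21 h, 7.0 with 18 to 24 h, and 8.2 when 10% of final recordings stop at 8 h.

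**The case against.** The strongest reply is that the trial is randomised, with readers and site personnel blinded. If recording lengths are similar in the two arms, raw counts lose precision but favour neither arm. This stands, and step 3 shows it. A reader might infer from the 0.93 figure that a 30% reduction would be hidden. It would be hidden only in the within-arm change, because placebo infants with the same lengths rise to 1.33. Even so, Table 3 reports the changes by arm and no contrast, and final recording length is observed after randomisation, so balance is likely but not assured.

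Four further points stand in whole or part.
- **Scope.** The whole-recording time base is explicit only for the pH-probe list. A reader might extend it to every reflux count, but the impedance counts share the problem only if the recording period in Section 4.6.1.2 means the full recording.
- **The 8-hour case.** Eight hours is a floor for evaluability, not the plan, and how often it would occur is not stated. The 3-fold figure is an extreme for a single infant.
- **Other measures.** Percentage time with pH below 4, percentage time with pH 4 to 6.9, and the mean clearance times do not grow with recording length. They are informative, but they do not count episodes, which is what the objective names. Symptomatic episodes linked to a detected reflux are compared by ANCOVA, but they are a different variable.
- **Descriptive analysis and the SAP.** Describing pharmacodynamic variables is a consistent choice, and the arm summaries let a reader see the difference. The SAP may define a rate. But the protocol itself states the time base, the summary and the method, so a SAP using rates and an arm comparison would depart from Table 3 as written.

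**Conclusion.** The point holds as a worthwhile improvement. As specified, the two pH-probe episode counts mix reflux with recording length, by +33% or −25% within the planned 18 to 24 h and by up to 3-fold if an 8 h recording is set against a 24 h one. These ratios use only the protocol's durations and a constant reflux rate.

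There are three consequences. Within-arm changes are distorted if final and baseline lengths differ systematically. The comparison of arms is noisier. That comparison is biased only if length differs by arm. The sizes in steps 2, 4 and 5 rest on assumed recording lengths, shares of short recordings and, in steps 4 and 5, reflux rates; they are illustrations, not forecasts.

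A reader might go further and conclude that the objective cannot be answered. The documents do not support that: nothing in them suggests that recording length will differ by arm, descriptive summaries by arm still show a difference, and several measures in the same block are free of the problem. What is missing is a stated estimate of that difference with its uncertainty, under an objective worded against placebo.

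**What to change.** In Sections 3.1.6 and 4.6.1.2 and in Table 3:

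1. Express the episode counts, including those longer than 5 minutes, as episodes per recorded hour (count ÷ recorded hours), or per 24 recorded hours (the same × 24), at both visits.
2. State the time base for the impedance counts, and scale them in the same way if it is the full recording.
3. Report the esomeprazole minus placebo difference in change with a 95% confidence interval, for example from the baseline-adjusted ANCOVA already planned for the other secondary counts.
4. As a sensitivity check, repeat the analysis on the 8-hour window common to both visits. Scaling assumes that a short recording represents the longer one; this check does not need that assumption.

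The percentage-time measures and mean clearance times can stay as they are. The cost is a little extra analysis, and recorded duration must be captured with the counts at each visit. No procedure for the infants changes.

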**Figure 1 Study flow chart**

**Table 1 Study summary of assessments and procedures**

Assessment/Procedure	Baseline Day -3 to Day 0	Randomization /Treatment Day 1-13	Study Completion/ Early Discontin- uation Day 14k	Safety Follow-up 14 days (+/-2 days) after final dosem
Informed consent	X			
Clinical assessment chart	X e	X e		
Medical history	X			
pH monitoring and impedance	X f		X l	
Cardiorespiratory monitoring	X		X	
Video monitoring	X f		X l	
Inclusion and exclusion criteria	X			
Vital signs a	X	X	X	X
Physical examination b	X	X i	X	X
ECG	X g			
Laboratory evaluation	X h		X	
Prior and concomitant medications	X	X	X	X
Dosing administration		X	X	
Randomization		X j		
Physician Global Assessment	X		X	
Adverse event assessment c	X	X	X	X
Serious adverse event assessment d	X	X	X	X

a Including temperature, blood pressure (BP), heart rate and respiration rate.

b Including weight, length and head circumference.

c Adverse events will be recorded from the day when the parents sign the informed consent. All ongoing AEs must be followed until resolution or until the investigator decides and documents that no further follow-up is necessary. AstraZeneca may request additional information about such AEs.

d Serious adverse events will be recorded from the day when the parents sign the informed consent.

e Baseline and final study day clinical assessment charts will be recorded during the 24 hour period before pH/impedance monitoring.

f pH/impedance/video monitoring begins once clinical assessment charts and other baseline procedures have been completed.

g Patients must have a normal ECG at baseline (historical documentation is acceptable) without clinically significant findings as deemed by the investigator.

h Stool hemocult performed at baseline only.

i Weight and length only.

j Randomization occurs on Day 1.

k Minimum of 10 days of treatment.

l Patients who discontinue early, prior to Day 10, will need to complete all final study procedures except video/pH/impedance monitoring.

m A post-study follow-up (in patient or office) safety assessment will occur 2 weeks following administration of the last dose of study drug for each patient.

## 3.2 Rationale and risk/benefit assessment

### 3.2.1 Rationale for study design, doses and control groups

This prospective study will employ a randomized, double-blind, placebo controlled design to evaluate the efficacy and safety of esomeprazole for the treatment of GERD in neonatal patients. The primary goal of the pharmacologic treatment of GERD is to reduce the exposure of the esophageal and supraesophageal mucosa to gastric acid by its effect on acid suppression. Currently available therapies for GERD include antacids, histamine-2 receptor antagonists (H2RAs), or proton pump inhibitors (PPIs), and prokinetic agents. Although antacids and the prokinetic agent, cisapride, have been shown to have modest efficacy in infants or children (Cucchiara et al 1984, 1987, Cohen et al 1999), their safety profiles do not support their use as primary therapies in infants (Rudolph et al 2001). In contrast, H2RAs have been considered front-line therapy (Cucchiara et al 2000) and various studies have demonstrated their efficacy in a pediatric population (Rudolph et al 2001).

The dosing of esomeprazole, 0.5 mg/kg, will be based on daily body weight. The rationale of exposure-response relationship was used to extrapolate the esomeprazole dose from adults to children. The esomeprazole exposure (AUC) and the response (efficacy and safety) for pediatric patients was estimated via a comprehensive PK and population PK modeling analysis of the omeprazole PK data in adult and pediatric patients and esomeprazole PK data in adults (Appendix C). The dose of 0.5 mg/kg/day is expected to provide a reasonable chance of efficacy while yielding potential exposures within the safety margin.

At the present time, there is limited safety data for doses of 0.5 mg/kg/day for the very young neonates (less than 5 days). However, data from a recently concluded study (AstraZeneca Clinical Study Report for Study SH-NEC-0001) in infants up to 24 months of age indicate no trends of clinical relevance regarding safety variables in relation to doses of esomeprazole 0.25 mg/kg or 1.0 mg/kg. In addition, preliminary population kinetics data from another study using the same dose of esomeprazole and same target population as Study SH-NEC-0001 do not indicate any safety concerns. For the reasons outlined above, our maximum proposed dose for neonatal studies dealing with pre-term and term neonates with GERD related symptoms will be 0.5 mg/kg/day.

PPIs have shown a remarkable tolerability profile in both adults and children. In an AstraZeneca omeprazole pediatric study (AstraZeneca Clinical Study Report No. 250, 2001), some children ages 0 months to 24 months inclusive had AUC exposures up to 3 times the mean exposure seen in adults administered the maximum labelled omeprazole dose (40 mg), and no drug-related side effects were reported. Additionally, examination of literature for the safety of the 2 PPIs with labelling for use in both pediatric patients and adults, omeprazole and lansoprazole, have not found any significant differences in safety between pediatric patients and adults at a similar exposure (AUC) (Scott 2002, Andersson 2000, Tran 2002, Gibbons 2003).

The use of a placebo group in the present study will provide the means to effectively analyze the efficacy and safety of esomeprazole therapy in an infantile GERD population. The

justification for allowing patients into the placebo arm is consistent with standards of medical practice which primarily include non-pharmacological treatments (ie, positioning and thickened feeds) for variable periods of time. It is at the discretion of the investigator to decide when pharmacological treatment is needed. Therefore, these patients will still receive non-pharmacological standard of care while on placebo.

Measurement of esophageal pH is a widely used method for establishing the diagnosis of GERD, in children as well as in adults. The method can also be used for evaluating the therapeutic effect of drugs, such as esomeprazole, in the treatment of GERD. Whereas esophageal pH only reflects acid related reflux, intraluminal impedance can be used to evaluate the total reflux pattern irrespective of pH. Thus, pH measurement in combination with intraluminal impedance measurement provides a more complete measure of the therapeutic response to a drug.

Orenstein's Infant Gastroesophageal Reflux Questionnaire (I-GERQ) is a questionnaire that has been validated in some populations of infants (Orenstein et al 1996). The clinical assessment charts used in this study are based upon this validated questionnaire. The actual questionnaire will not be used in this study.

The study personnel will administer the investigational product thus ensuring treatment compliance.

